5.5.2 Unexpected Events Defined

An unexpected event is any adverse drug experience or unanticipated adverse device effect, the specificity or severity of which is not consistent with the current approved product labeling (package insert) for the test article, the Investigator's Brochure, or as described in the clinical protocol and consent materials. This includes an increase in the frequency or severity of a previously reported adverse event that is significantly above the rates known from previous experience with the test article.

5.5.3 Relatedness of Event to Test Article or Procedure

The Investigator (or an authorized study physician) must submit an attribution for the relatedness of the reported adverse event to the test article or procedure.

The attribution should take into account both the temporal association and any known physical, physiological or toxicological information regarding the test article that could reasonably infer causality. Relatedness should only be considered for the experimental test article and not for any standard study examination or diagnostic procedures. The five attribution categories are:

- Definite—*Clearly related* to test article or procedure.
- Probable—*Likely related* to test article or procedure.
- Possible—*May be related* to test article or procedure.
- Remotely—*Unlikely related* to test article or procedure.
- Unrelated—*Clearly NOT related* to test article or procedure.

5.6 Withdrawal Criteria

Participants may choose to withdraw from this study for any reason at any time without penalty or prohibition from enrolling in other clinical protocols.

If a participant withdraws from the study completely, they should return for a safety visit at least 1 month after withdrawing. All 30-month assessments/examinations should be included in the safety visit.

6 Statistical Considerations

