Secondary Endpoints(s):	Secondary efficacy variables will include: mean change from baseline value in Humphrey Visual Field Sensitivity (VFS) from baseline to 24 months, mean change in “5-point” VFS from baseline to 24 months (using the 5 retinal points with greatest average change), mean change from baseline in Best Corrected Visual Acuity (BCVA) at 12, 18, 24, 30 and 36 months, and changes in ERG, Optical Coherence Tomography (OCT), clinical grades of inflammation (anterior chamber cell and vitreous haze grades), and vision-related quality of life (NEI-VFQ25) at each visit.
Safety Endpoint(s):	Safety variables will include the incidence of adverse events, changes in vital signs, marked changes in clinical laboratory data, ECG abnormalities, and findings during physical examinations through 36 months
# of Clinical Sites:	This is a single investigator study; Retinal Degenerations Clinic at the University of California, San Francisco
# of Study Subjects:	Approximately 30
Inclusion Criteria:	
1. Participant must be between 18 and 55 years of age.2. Participant must have a diagnosis of retinitis pigmentosa or Usher syndrome type 2 or 3.3. Participant must understand and sign the protocol informed consent. If the participant’s vision is impaired to the point where he/she cannot read the informed consent document, the document will be read to the participant in its entirety.4. Best-corrected visual acuity must be no worse than 20/63 (at least 59 letters).5. Participants must have clear natural lenses.6. Participants must have less than 6 diopters myopia.7. Participants must be medically able to undergo ophthalmic surgery for the NT-501 device insertion and able to undergo all assessments and tests associated with the protocol.

8. Females of childbearing potential (women with last menses \leq 1 year prior to screening) must agree to use an effective form of birth control from study onset until they complete the study.
9. Participants must have reproducible baseline AOSLO image montages at 2 baseline imaging sessions with quality suitable to identify a minimum of 7 regions of interest (ROIs) at which reliable cone spacing and/or density measures can be made over the central 5.7 degrees.
10. Participants must have interocular symmetry of disease severity as measured by cone spacing, with a difference of less than 2 standard deviations in average cone spacing z-scores at the selected ROIs between the 2 eyes.

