Implant Surgery					X								
LABORATORY													
Serum chemistry , hematology, urinalysis			X ³						X		X		X
Urine Pregnancy ⁶			X ³						X		X		X
HIV testing			X ³										
Genetic testing through eyeGENE			X ⁷										
Serum for antibody/CNTF concentration			X						X		X	X	X

¹ Baseline 1 Screening will occur within 7 weeks of implant surgery; Baseline 2 Screening will occur within 4 weeks of Baseline 1.

² Baseline 3 will occur < 4 days prior to implant surgery

³ ECG and pre-op laboratory testing should be performed within the timeframe mandated by the OR.

⁴ Measurement or exams should be taken at any point within 7 weeks preceding implant surgery.

⁵ Measurement at Baseline 1 must establish a minimum of 7 ROI's; measurement at Baseline 2 must verify a minimum of 7 of the previously established ROI's for measurement throughout the study period.

⁶ Urine pregnancy test will only be performed on premenopausal women.

⁷ Genetic testing will be offered to patients with diseases for which eyeGENE offers testing. Separate consent is required and patients can refuse to submit blood for genetic testing but still participate in the present study.

Photoreceptor Structure in a Phase 2 Study of Encapsulated Human NTC-201 Cell Implants Releasing Ciliary Neurotrophic Factor (CNTF) for Participants with Retinitis Pigmentosa Using Rates of Change in Cone Spacing and Density as the Primary Outcome

1 Background and Rationale

Retinitis Pigmentosa (RP) is a group of hereditary disorders whose common feature is a progressive deterioration of the rod and cone photoreceptors in the retina, which results in the reduction and loss of both peripheral and central vision. Histopathologic studies in naturally occurring and genetically engineered animal models of photoreceptor dysfunction and death in the condition termed retinitis pigmentosa (RP) have indicated the promise of ciliary neurotrophic factor (CNTF) as an effective therapeutic agent for reducing photoreceptor loss associated with degeneration of the cells of the outer retina. CNTF is one of several neurotrophic factors that are produced endogenously by neurons or supporting glial cells and has been demonstrated to be highly effective in retarding photoreceptor neuron loss in 12 animal RP models with various forms of retinal degeneration.

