- Assuming a recommendation to continue enrollment results from the SMC's review of safety data (up to one month post implant), the second patient will undergo surgical implantation of the investigational product during day's 1 – 5 of week 5.
- The 2-month post implant safety data for patients 1 and the one-month post-implant safety data for patient 2 will be supplied to the chairman of the SMC at the beginning of week 9.

The SMC's recommendation was to continue enrollment following the SMC review of safety data (up to two month post implant). The remaining patients will undergo surgical implantation of the investigational product in accordance with enrollment.

Devices will not be explanted except in instances where it is medically advised due to an adverse event. An examination for safety will occur one day following surgical implant and periodically thereafter.

All participants will be followed clinically for 30 months.

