4.1 Outcomes

Primary Outcome:

The primary outcome is rate of change in cone spacing and rate of change in cone density as determined using AOSLO images of regions of interest (ROIs) preselected at baseline in eyes treated with CNTF compared to contralateral eyes treated with sham surgery over 30 months. Cone spacing and density will be measured by 3 independent graders who will remain fully masked to the treatment assignment throughout the duration of the trial. We will compare rates of change in cone spacing and cone density between CNTF-treated and contralateral sham-treated eyes through 30-months using pooled linear regression.

Secondary Outcomes:

Secondary outcome measures will involve comparing rates of change in standardized measures of visual function between CNTF- and sham-treated eyes. Secondary outcomes will include the following functional and structural assessments: mean and median change in best spectacle-corrected visual acuity (BCVA) using the ETDRS protocol, changes in visual field sensitivity and foveal sensitivity in decibels (dB) using automated static perimetry using the Humphrey visual field 10-2 protocol and rod and cone-mediated fundus-guided microperimetry using a modified Nidek MP1, changes in thickness of the outer nuclear layer (ONL) and outer segment plus RPE (OS+) layer thickness as measured using spectral-domain optical coherence tomography (SD-OCT), and changes in full-field ERG scotopic and photopic standard a- and b-wave amplitudes and timing from baseline to 36 months. All parameters except full-field ERG will be measured at 6, 12, 18, 24, 30 and 36 months after implant surgery; standard full-field ERG will be performed according to ISCEV standards at baseline, 12, and 24 months.

Safety Outcomes:

Safety of the NT-501 ECT technology implant has been demonstrated in prior Phase 1 and Phase 2 trials of the implant. Separately from efficacy outcomes which demonstrate a reduction or increase in function, safety parameters will continue to be collected and assessed by the following outcomes (occurrence of these outcomes does not necessarily require explant):

- Rejection or extrusion of the NT-501 device.
- Protocol-related abnormal findings from serum chemistry, hematology, and urinalysis (those abnormal findings that are determined to be clinically significant by the Principal Investigator).

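### The withdrawal visit copies the month-30 assessments, which in Table 1 include no chemistry, hematology or urinalysis, so a participant who withdraws before month 12 has no scheduled post-implant safety panel

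*Protocol*

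**What the plan says.** Protocol Section 5.6 covers complete withdrawal. On timing it says that "they should return for a safety visit at least 1 month after withdrawing"; on content, "All 30-month assessments/examinations should be included in the safety visit". The exit visit has no test list of its own, so Table 1 supplies it.

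The laboratory block of Table 1 has a row "Serum chemistry , hematology, urinalysis", a urine pregnancy row (footnote: "Urine pregnancy test will only be performed on premenopausal women") and a row "Serum for antibody/CNTF concentration", besides HIV and genetic testing before surgery.

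The laboratory tests serve a stated purpose. Section 4.1 names "Protocol-related abnormal findings from serum chemistry, hematology, and urinalysis" as a safety outcome, limited to those the Principal Investigator judges clinically significant. The Protocol Summary lists marked laboratory changes among the safety endpoints, and its sentence ends "findings during physical examinations through 36 months". Section 6.3 repeats the laboratory variable without a time limit. SAP Section 2.3.1 says that safety will also be judged on other laboratory measurements and sets a study period of 36 months.

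On length of follow-up, Protocol Section 4 says "All participants will be followed clinically for 30 months", while the last column of Table 1 is month 36.

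**The concern.** An exit visit is usually the last chance to collect safety data on someone who leaves. Here its content is borrowed from a visit that, in Table 1, is not the last one and does not carry the safety laboratory panel. A site following Section 5.6 to the letter would draw serum for antibody and CNTF levels but would have no instruction to run chemistry, hematology, urinalysis or the pregnancy test.

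What is at stake is the completeness of a named safety outcome. Protocol Section 6.2 bases the safety analyses on all randomized patients, so a missing panel in a leaver is a gap in the intended analysis set. Under Section 4 the device comes out only when an adverse event makes removal medically advisable, so some leavers may go home with the implant in place. In a trial of about 30 participants, a few missing panels are a visible share of the laboratory data.

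**Working it through.** The plan gives no figure to reproduce here. The check is a column reading of Table 1, set beside Section 5.6, followed by a bound on the number affected.

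**Step 1: locate the tests.** Table 1 has 13 visit columns: Baseline 1, Baseline 2, Baseline 3, Implant Surgery, 1 day, 1 week, 1 month, and months 6, 12, 18, 24, 30 and 36. Counting cell positions in the extracted rows gives:

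| Row | Marked at | Month 30? |
|---|---|---|
| Chemistry, hematology, urinalysis | Baseline 3, months 12, 24, 36 | No |
| Urine pregnancy | Baseline 3, months 12, 24, 36 | No |
| Antibody/CNTF serum | Baseline 3, months 12, 24, 30, 36 | Yes |
| HIV | Baseline 3 | No |

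**Step 2: test the reading.** Each of these rows fills all 13 positions. The adverse event row, counted the same way, runs from 1 day to month 36 as expected. The chemistry row has a regular yearly pattern ending at month 36, and differs from the antibody row only at month 30. Two other rows fit less well. The Implant Surgery mark falls under 1 day post-op, and ERG falls at Baseline 3 and months 6 and 18, whereas Section 4.1 gives baseline, 12 and 24 months. The laboratory reading is therefore probable, and should be confirmed in the original PDF.

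**Step 3: apply Section 5.6.** For a participant who withdraws after surgery and attends the exit visit:

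| Withdrawal | Scheduled post-implant panels before leaving | Panel at exit | Most recent panel |
|---|---|---|---|
| Before month 12 | 0 | 0 | Baseline 3 (pre-implant) |
| Between months 12 and 24 | 1 | 0 | Month 12 |
| Between months 24 and 36 | 2 | 0 | Month 24 |

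Because the exit visit comes at least 1 month after withdrawal, someone leaving at month 23, for example, is seen at month 23 + 1 = 24 or later, with a last panel at month 12: a gap of at least 24 − 12 = 12 months.

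**Step 4: bound the number.** SAP Section 3.1.4 allows 15% loss to follow-up. With about 30 participants (Protocol Section 4), 0.15 × 30 = 4.5; with the 20 in SAP Section 3.1.5, 0.15 × 20 = 3. The allowance covers the whole study. Neither document says how much of it falls before month 12, or how many of those people would return for an exit visit. Taking the allowance as a ceiling, the range is 0 to about 4 to 5 of 30.

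**Step 5: compare the time horizons.** Protocol Sections 4 (follow-up sentence) and 5.6 point to month 30. Table 1, the Protocol Summary safety endpoint and SAP Section 2.3.1 run to month 36. If Section 5.6 was meant to refer to the final visit, the panel belongs in the exit visit, because month 36 carries it. If it literally means month 30, the panel is absent. The text does not settle which.

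**The case against.** The strongest reply is that this is an out-of-date visit reference affecting an unknown, possibly zero, number of people, with no bearing on the primary analysis. Several parts of that reply stand.

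- **Some laboratory data are collected at exit.** A reader might infer that an early leaver has no post-implant laboratory data at all. That is too broad: the antibody/CNTF serum is marked at month 30. Section 5.6 also does not forbid unscheduled tests.
- **Ocular testing at exit is not complete either.** A reader might picture every eye test being done while only the laboratory tests are skipped. ERG is not marked at month 30 in the extracted table, and Section 4.1 does not schedule it there.
- **The 15% is not an estimate of those affected.** It covers the whole study and includes people who never return, for whom a reworded Section 5.6 gains nothing.
- **Bias towards safety is not shown.** A reader might infer that leavers are those with problems, so that the laboratory results look too favorable. Section 5.6 allows withdrawal for any reason, no passage links leaving to laboratory abnormality, and SAP Section 7.7 does not list a laboratory summary.
- **Adverse event rules cover part of the ground.** Section 5.5 counts a clinically significant laboratory abnormality as an adverse event, and Section 5.3 follows events after early withdrawal until resolved or for 30 days after the final visit. But an abnormality without symptoms is found only if the test is run.
- **Loss of the month-36 visit for everyone is speculative.** A reader might take the 30-month sentence in Section 4 to mean that sites would skip month 36. That supposes a single site ignoring a column of its own visit schedule.

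None of this supplies the missing panel. The rule for the exit visit, read with Table 1, still omits it.

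**Conclusion.** The point holds for scheduled chemistry, hematology, urinalysis and the urine pregnancy test, and no further. Under Section 5.6 with Table 1, a participant who withdraws after surgery but before month 12 has zero scheduled post-implant panels, and later leavers exit on their previous annual one. This leaves a hole in a safety outcome that Section 4.1 names.

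The number of early leavers without any panel is 0 to about 4 to 5 of 30, conditional on the SAP's allowance being a fair ceiling. The conclusion also assumes that the extracted laboratory rows match the original table, that Section 5.6 is applied literally, and that no unscheduled tests are ordered. The documents support a claim of missing data; they do not support one about the direction of bias. The correction is worth making because it is cheap and because the 30- and 36-month statements need reconciling in any case.

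**What to change.** Confirm the laboratory rows of Table 1 against the original PDF. Then reconcile Section 5.6 and the 30-month follow-up sentence in Section 4 with Table 1, the 36-month safety endpoint in the Protocol Summary and the 36-month study period in SAP Section 2.3.1. The direct way is to point the Section 5.6 exit visit to the final (month 36) assessments of Table 1. That brings in the safety laboratory panel and, where applicable, the pregnancy test, and keeps the antibody/CNTF sample, which is also marked at month 36.

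The cost is a short protocol amendment and one extra blood and urine set per withdrawing participant, at a visit that already takes place and already draws serum. It will not recover data from people who do not return.

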6.1 Description of Trial

10 subjects will be enrolled into the study. Both eyes of each participant will be evaluated in this study. There are, thus, a minimum of 10 participants and a minimum of 20 eyes in the trial. One eye of each participant will be randomly assigned to receive CNTF, and the fellow eye will receive sham surgery. AOSLO montages will be acquired at baseline 1 covering the central 5.7 degrees to identify at least 7 ROIs where unambiguous cone mosaics are visualized. AOSLO images will be acquired at Baseline 2 within 1 month of Baseline 1 and focused on the ROIs. Humphrey visual field sensitivity of each eye will be measured at baseline, month 6, month 12, month 18, month 24 and month 30. The total score for the entire retina, averaged across replicates, will serve as the unit of analysis for baseline qualifications and efficacy outcomes. In addition, the 5 points of the visual field with the greatest change during treatment will serve as a key secondary efficacy variable. Pupil size will be recorded during HVF assessment.

6.2 Analysis Populations

Efficacy and safety analyses will be based on all randomized patients, in accordance with the intent-to-treat principle. Secondary analyses will be performed in the subgroup of patients who are in full compliance with protocol, have a favorable surgical outcome and no evidence of cataracts at 30 months.

6.3 Efficacy and Safety Variables

The primary efficacy variable is the rate of change in cone spacing and cone density from baseline to 24 months. Secondary efficacy variables will include: mean change from baseline value in Humphrey Visual Field Sensitivity (VFS) from baseline to 24 months, mean change in “5-point” VFS from baseline to month 24 (using the 5 retinal points with greatest average change), mean change from baseline in Best Corrected Visual Acuity (BCVA) at 12, 18, and 24 months, and changes in ERG, Optical Coherence Tomography (OCT), clinical grades of

inflammation (anterior chamber cell and vitreous haze grades), and vision-related quality of life (NEI-VFQ25) at each visit.

The mean change in VFS will be calculated using the sum of all points at baseline and each follow-up visit. Likewise, the 5 points with greatest change from baseline will be selected for each patient based on the average score per point across replicates at baseline and at month 24; the mean of these 5 points will be used to compute the change from baseline in “5-point” VFS.

Safety variables will include the incidence of adverse events, changes in vital signs, marked changes in clinical laboratory data, ECG abnormalities, and findings during physical examinations.

6.4 Sample Size Rationale

The primary analysis will compare the mean rate of change in cone spacing and cone density between CNTF-treated and control eyes over the 24-month study period using pooled linear regression. With a minimum 10 patients the sample size will provide in excess of 80% power to detect a difference of 0.084 arcminutes in cone spacing (twice the effect reported per year in preliminary studies (Talcott et al, 2010), assuming a within-region standard deviation of 0.11 (based on preliminary data, and using a paired-subjects t-test as a basis for power calculations).

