3.1.2 Power

We plan recruitment of sufficient subjects for an 80% power to detect an effect size of 0.084 arcminutes over two years.

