3.1.3 Statistical Properties of the Primary Outcome

Based on our preliminary study, we expect the standard deviation in the difference between the regression slopes to be approximately 0.11 arcminutes.

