3.1.5 Sample size calculation methodology

We used a simplified version of the analysis we plan in order to estimate the power for the more complex analysis. This reduces the analysis to a paired T-test. More specifically, we determined the rate of change over time of the cone spacing in our pilot patients, and computed a pooled standard deviation over all these regions (in untreated persons) from which we derived an expected standard deviation of the difference in the total change in cone spacing after two years of approximately 0.11. Using the standard formula for the sample size of a one-sample T-test

(e.g. Chow et al, 2007, formula 3.1.2), we find we would need a total of 17 individuals per group, or 20 adjusting for loss to follow-up.

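### The protocol's claim of over 80% power at 10 patients and the SAP's requirement of 17 use the same 0.084 and 0.11 but cannot share one meaning of 0.11, and the planned N is 10, 20 or about 30

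*Protocol*

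**What the plan says.** **Protocol 6.4** claims the following for a paired t-test: "With a minimum 10 patients the sample size will provide in excess of 80% power to detect a difference of 0.084 arcminutes". The difference is described as "twice the effect reported per year in preliminary studies", so 0.084 is a two-year figure. The SD enters as "assuming a within-region standard deviation of 0.11". The section gives no alpha, no number of regions and no correlation between regions.

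**SAP 3.1.1 to 3.1.5** plans for "an 80% power to detect an effect size of 0.084 arcminutes over two years" at two-sided 0.05, with 15% loss to follow-up. Section 3.1.3 describes the SD this way: "we expect the standard deviation in the difference between the regression slopes to be approximately 0.11 arcminutes". Section 3.1.5 says the pilot analysis "computed a pooled standard deviation over all these regions" in untreated persons, and that from it "we derived an expected standard deviation of the difference in the total change in cone spacing after two years of approximately 0.11". It concludes: "we find we would need a total of 17 individuals per group, or 20 adjusting for loss to follow-up".

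**Number of participants.**
- Protocol 6.1 says that 10 will be enrolled and then calls 10 a minimum.
- The Protocol Summary and Section 4 say approximately 30. The first two cohorts in Section 4, of 9 and 6, already total 15.
- SAP 3.1.5 arrives at 20.
- SAP 3.3 shuffles ten right-eye and ten left-eye assignments, which makes a list of 20.

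**The concern.** Two documents for one trial take the same effect, the same nominal SD and the same test, and reach sample sizes that differ by a factor of 1.7 (17 against 10) before any allowance for loss. At least one statement must be wrong, or 0.11 must mean different things in the two places. The number is in fact described in three ways: a within-region SD, the SD of a difference between slopes with no time unit, and the SD of the between-eye difference in two-year change.

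The power rationale for the primary endpoint therefore has no defined variance input, and a reader cannot tell which N it supports. There is an operational consequence too: if about 30 are enrolled, the list described in SAP 3.3 ends at 20.

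**Working it through.** **Inputs.** Difference 0.084 arcmin over two years (Protocol 6.4, SAP 3.1.2); SD 0.11 (Protocol 6.4, SAP 3.1.3 and 3.1.5); two-sided alpha 0.05 (SAP 3.1.1); 15% loss (SAP 3.1.4); at least 7 regions per eye (Protocol 4.7).

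**Method.** Paired (one-sample) t-test on treated-minus-sham differences: df = n − 1, noncentrality = d√n, d = difference / SD. Here d = 0.084 / 0.11 = 0.764. All n below are evaluable participants.

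**Step 1: the SAP's figure.**

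| n | Power |
|---|---|
| 10 | 57.7% |
| 16 | 81.4% |
| 17 | 84.0% |
| 20 | 89.9% |
| 30 | 98.1% |

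With SD exactly 0.11, 80% is first reached at 16. Seventeen is the smallest adequate n when d lies between 0.724 (80% at n = 17) and 0.749 (80% at n = 16). That is an SD between 0.084/0.749 = 0.112 and 0.084/0.724 = 0.116, which overlaps the values that round to 0.11. Then 17 / 0.85 = 20. The SAP figures hold.

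**Step 2: the protocol's figure.** On the same definition, power at 10 is 57.7%. Letting the SD run from 0.105 to 0.115 moves it only from 61.6% to 54.0%. The protocol's 10 also carries no allowance for loss: 10 × 0.85 = 8.5, and power is 46.2% at 8 and 52.1% at 9.

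**Step 3: can one SD satisfy both?** For 80% at n = 10, d must be 0.996, so the SD can be at most 0.084 / 0.996 = 0.0843, or 77% of 0.11. The SAP's 17 needs 0.112 to 0.116. The ranges do not overlap.

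**Step 4: could averaging over regions rescue the protocol?** SAP 7.5.1.1 averages change scores over regions within each eye. If 0.11 is a per-region SD and k equally correlated regions are averaged, the SD becomes s√((1 + (k − 1)ρ)/k). The documents give no ρ, so the values below are assumptions, with k = 7 and n = 10.

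| Reading of 0.11 | Power at n = 10 | 80% lost above |
|---|---|---|
| Per-region SD of the paired difference, s = 0.11 | 94.8% (ρ = 0.25), 81.1% (0.5), 68.0% (0.75) | ρ = 0.52 |
| Per-region SD in one eye, eyes independent, s = 0.11√2 | 88.7% (ρ = 0.1), 72.1% (0.25), 52.2% (0.5) | ρ = 0.18 |

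More than 80% at 10 is therefore possible, but only below a threshold correlation that is never stated. Wherever it is achieved, the SD of the averaged difference is at most 0.0843 and 10 participants suffice, so the SAP's 17 would be too many.

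**Step 5: the slope wording in SAP 3.1.3.** If the slope difference were per year (an assumption), the two-year SD would be 2 × 0.11 = 0.22 and d = 0.382. Power would be 19.1% at 10, 36.8% at 20 and 52.5% at 30.

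**Step 6: a related figure.** SAP 3.2 gives 1.02 as the standardized visual-acuity effect detectable at 80% power, without an n. At unadjusted 0.05 the detectable effect is 1.00 at n = 10, 0.72 at 17 and 0.66 at 20. At the first Holm step (0.05/6) it is 0.95 at 17 and 0.86 at 20. The 1.02 fits neither 17 nor 20.

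**The case against.** The best defence is that the two documents label the SD differently. The protocol's is within-region and the SAP's is the between-eye difference in two-year change, so the 58% comes from carrying the SAP's definition into the protocol. That is fair, and it means the protocol's figure is not shown to be impossible. It does not reconcile the documents. The protocol states no averaging, region count or correlation, and both power texts present the same 0.084 and 0.11.

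A second point is that SAP 3.1.3 gives its SD in arcminutes, not arcminutes per year, and that SAP 3.1.5 converts to a two-year total. This makes the per-year reading in step 5 the least likely one. It stands only as a reason to state the time unit.

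Third, the figures at 20 and 30 are for evaluable participants. With 15% loss, 20 enrolled leaves 17 (84.0%) and 30 enrolled leaves 25 or 26 (about 96%). Pooling all of about 30 also combines the two implant outputs described in Protocol Section 4. These qualifications are right and leave the contradiction as it is.

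Fourth, SAP 7.5.1.1 plans a rank test on z-scores at 36 months, while the power calculation is a two-year t-test that SAP 3.1.5 itself calls simplified. Correcting the arithmetic therefore does not give power for the planned test. That limits what the fix achieves but does not excuse two incompatible versions of the simplified calculation.

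Finally, randomization rows can readily be added, and the documents do not show whether they were. The plan as written still provides only 20.

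**Conclusion.** The concern holds. No single SD of the paired difference supports both more than 80% power at 10 and a requirement of 17: the first needs at most 0.0843, the second 0.112 to 0.116. On the SAP 3.1.5 definition, with two-sided 0.05 and an exact paired t-test, power at 10 evaluable participants is 57.7%. The protocol's claim could be true only if 0.11 is a per-region SD, averaging is applied on top of it, and the between-region correlation is at most about 0.5 (0.11 a paired difference) or 0.2 (0.11 a single-eye SD). These thresholds assume 7 equally correlated regions.

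This is an undefined input and a contradiction between documents. It is not evidence that the trial is underpowered at 20 or about 30, where the SAP's inputs give 84% and about 96% after 15% loss. The planned N of 10, 20 and about 30 is unreconciled in its own right, and a 20-row list does not cover the largest. It must be fixed, because the sample size justification for the primary endpoint cannot be relied on as written.

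**What to change.** 1. **Define 0.11 once**, identically in Protocol 6.4, SAP 3.1.3 and SAP 3.1.5: region, eye or person level; one eye or the treated-minus-sham difference; per year or over two years; before or after averaging over regions. Show how it comes from the pilot data.
2. **Restate power.** Put two-sided alpha 0.05 in Protocol 6.4 and give power at the planned N, saying whether n is enrolled or evaluable. If the SAP 3.1.5 definition stands, replace the claim at 10 with about 58% and cite 17 (20 with 15% loss) for 80%. If averaging applies on top of 0.11, state the number of regions and the assumed correlation, show the result, and revise SAP 3.1.5 to agree.
3. **State one planned N** in the Protocol Summary, Section 4, Section 6.1 and the SAP, and make the SAP 3.3 list cover it.
4. **In SAP 3.2**, recompute the visual-acuity effect at that N and say whether the Holm correction was applied.

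The cost is text and arithmetic, plus extra randomization rows if N exceeds 20. No participants need be added if the planned N is 20 or about 30. If it is 10, either the power claim or the N may have to change, depending on how 0.11 is defined.
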